Cohort 1 used FD003 to monitor a change in volume induced by the infusion of 350 ml of 5% albumin solution given over 30 minutes. At 5 minutes post completion of the infusion, the average plasma volume increase was 324 ml with an SD of 49mL, showing excellent accuracy for following a change in plasma volume. By 30 minutes post infusion, the average volume increase from baseline was reduced to 224ml showing that FD003 was being retained within the vasculature even though the 5% Albumin solution was slowly distributing into the interstitial space. This cohort was not used for PK due to the complication of accounting for the additional volume infused.

The FAST VFI was generally safe and well tolerated in healthy patients in Cohorts 1 and 2 and in patients with impaired renal function in Cohorts 3 and 4. No severe or serious TEAEs, TEAEs leading to study drug discontinuation, or deaths were reported during the study. Overall, the majority of TEAEs reported were mild in severity. Three patients in Cohort 4 had a TEAE of blood creatine phosphokinase increased related to clinically significant abnormal creatine kinase levels. All 3 TEAEs of blood creatine phosphokinase increased were mild in severity and considered by the investigator to be possibly related to study drug. There were no other clinically significant abnormal clinical laboratory values. There were no clinically significant abnormal ECG or vital signs measurements, nor were there clinically meaningful trends identified in observed values or changes from baseline. There were no clinically significant abnormal physical examination findings.

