## 7.2 Derived Parameters

The following formulas will be used for determination of estimated and measured TBV, ideal TBV, estimated and measured total blood volume status (eTBVS and mTBVS), ePV, estimated PV change, ideal PV, estimated and measured plasma volume status (ePVS and mPVS), and eGFR on day 1 and day 3:

Nadler formula for eTBV (Sharma & Sharma, 2020):

- Men:  $eTBV [L] = (0.3669 \times \text{Height [m]}^3) + (0.03219 \times \text{Weight [kg]}) + 0.6041$
- Women:  $eTBV [L] = (0.3561 \times \text{Height [m]}^3) + (0.03308 \times \text{Weight [kg]}) + 0.1833$

mTBV will be calculated as follows:

- $mTBV [mL] = mPV [mL] / (1 - \text{hematocrit [\%]} / 100)$

Lemmens-Bernstein-Brodsky formula for ideal TBV (iTBV) (Lemmens, Bernstein, & Brodsky, 2006):

- $iTBV [mL/kg] = 70 / [\text{sqrt}(\text{body mass index}/22)]$  – the lowest body weight during the days 1 to 5 will be used for calculation of BMI
- $iTBV [mL] = iTBV [ml/kg] \times \text{weight [kg]}$  – the lowest body weight during the days 1 to 5 will be used for calculation

Estimated and measured total blood volume status:

- $eTBVS [\%] = \text{Percentage change from iTBV: } (eTBV - iTBV) / iTBV$
- $mTBVS [\%] = \text{Percentage change from iTBV: } (mTBV - iTBV) / iTBV$

Kaplan-Hakim Formula for ePV (Ling et al., 2015):

- Men:  $ePV [mL] = (1 - \text{hematocrit [\%]}) \times [1530 + (41 \times \text{weight [kg]})]$
- Women:  $ePV [mL] = (1 - \text{hematocrit [\%]}) \times [864 + (47.9 \times \text{weight [kg]})]$

Strauss formula for plasma volume change (Strauss, Davis, Rosenbaum, & Rossmeis, 1951):

- $PV\_2/PV\_1 \times 100 [\%] = \text{hemoglobin\_1 [g/dL]} / \text{hemoglobin\_2 [g/dL]} \times (1 - \text{hematocrit\_2 [\%]}) / (1 - \text{hematocrit\_1 [\%]}) \times 100$

Plasma volume change will also be calculated via the ratios of ePV by the Kaplan-Hakim-Formula

Harrison formula for ideal PV (iPV) (from Ling 2015):

- Men: iPV [mL] = 39 [mL/kg] × weight [kg] – the lowest body weight during the days 1 to 5 will be used for calculation
- Women: iPV [mL] = 40 [mL/kg] × weight [kg] – the lowest body weight during the days 1 to 5 will be used for calculation

Estimated and measured plasma volume status (ePVS and mPVS):

- ePVS [%] = Percentage change from iPV: (ePV - iPV)/iPV
- mPVS [%] = Percentage change from iPV: (mPV - iPV)/iPV

The eGFR will be calculated using CKD-EPI formula (Levey et al., 2009):

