### 7.7 Secondary analyses

#### 7.7.1 Efficacy

To evaluate how estimated PV (ePV) and estimated total blood volume (eTBV) assessments on days 1 and 3 (by Nadler's formula, Kaplan-Hakim formula) predict measured PV (mPV; as assessed by FAST methodology) and measured TBV (mTBV; calculated from mPV and measured hematocrit) at these time points, linear regression models with the measured values at a given day as dependent variable and the estimated version as independent variable will be generated. The models will be adjusted for BMI, weight, and height separately.

Further, Bland-Altman plots will be generated comparing the estimated and measured parameters separately for day 1 and day 3. The defined limits of agreement are  $\pm 500\text{ml}$  for TBV and  $\pm 300\text{ml}$  and for PV. The amount of values within 15% and within 30% of the measured values will also be determined. In addition, the diagnostic test accuracy including 95% confidence interval as proposed by Obuchowski (Obuchowski, 2005) will be calculated. The interpretation for a continuous reference standard is as follows: Of two randomly chosen patients, the diagnostic accuracy is the probability that the patient with the higher reference standard result has a higher diagnostic test result than the patient with the lower reference standard test result. In the case of the study, the measured PV and TBV will act as reference standard while the estimated versions serve the diagnostic test.

To evaluate how a clinical evaluation on days 1 and 3 predicts mPV and mTBV at these time points, linear regression models will be used.

Depending on the amount of available information and distribution, the following parameters will be considered for the analysis in the order of appearance: hematocrit (only PV), mean arterial blood pressure, BMI (only PV), weight, height (BMI, weight, height will be entered in 3 separate models), age, gender, NYHA stage, respiratory rate, edema grade, presence of pulmonary rales, jugular venous congestion. At least 10 observations will be needed per parameter that need to be estimated. Bland-Altman plots, frequencies within 15% and 30%, and diagnostic accuracy will be evaluated as stated before.

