To evaluate whether patients with a high mPVS ( $> +10\%$ ) or a high mTBVS ( $> +10\%$ ) on day 1 and/or day 3 are at risk of being refractory to diuretic therapy (defined as any dosage increases of furosemide i.v. dose equivalent, adding thiazide after day 1, require ultrafiltration/RRT within the next 24-48 hours, fail to improve subjectively in PGA and dyspnea scales, fail of mean weight loss during the study period Day 1-Day 5 of at least 0,5 kg/d) logistic regression models using mPV and mTBV as independent variables will be used.

To evaluate whether the changes of ePV (using relative and absolute change as well as the Strauss' formula) and eTBV (using relative and absolute change) from day 1 to day 3 adequately reflects the changes of mPV and mTBV Bland-Altman plots will be generated. These plots will be analysed exploratory, since no appropriate values for limits of agreements are available. The amount of values within 10% and within 30% of the measured values will also be determined. In addition, the diagnostic test accuracy including 95% confidence interval as proposed by Obuchowski will be calculated.

To evaluate whether the change of mPV and mTBV and changes of mPVS and mTBVS from day 1 to day 3 as well as the mPVS and mTBVS on Day 1 and Day 3 is predictive of the remaining length of stay at the given day (i.e. remaining length of stay starting with day 1 or with day 3), dialysis/ultrafiltration requirement, or rehospitalization within 30 days, or mortality, linear (remaining length of stay), logistic (dialysis/ultrafiltration, rehospitalization within 30 days) or Cox-regression models (mortality) will be utilized using changes of mPV and mTBV from day 1 to day 3 (first model), changes of mPVS and mTBVS from day 1 to day 3 (second model), and mPVS and mTBVS at day 1 (third model) and day 3 (fourth model) as independent variables.

To evaluate whether the percentage changes of mGFR from day 1 to day 3 ( $< 0$  vs.  $\geq 0$ ; continuous) predicts the percentage changes of eGFR from day 2 to day 4 (CKD-EPI formula only;  $< 0$  vs.  $\geq 0$ ; continuous), a logistic as well as a linear regression model will be used.

The same will be done to investigate the changes in eGFR from day 1 to day 3 (all formulas) as the dependent variable. Further, exploratory Bland-Altman plots without predefined limits of agreement will be created.

To evaluate whether patients with a high PVS or TBVS on Day 1 ( $> +10\%$ ) and a decreasing PVS

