or TBVS between Day 1 and 3 had significantly different percentage change of mGFR between Day 1 and Day 3 compared to patients with a high PVS or TBVS and an increasing PVS between Day 1 and 3, t-Tests or Mann-Whitney-U-tests will be used depending on the distribution of the values.

To evaluate whether Patients with a low PVS or TBVS on Day 1 (<-10%) and an increasing PVS or TBVS between Day 1 and 3 had significantly different percentage change of mGFR between Day 1 and Day 3 compared to patients with a low PVS or BCS and a decreasing PVS between Day 1 and 3, t-Tests or Mann-Whitney-U-tests will be used depending on the distribution of the values.

To evaluate whether patients with an improving (i.e. increasing) mGFR from day 1 to day 3 differ significantly from patients with a worsening (i.e. decreasing) mGFR regarding baseline characteristics (see chapter 4.1), mPVS, mTBVS, ePVS, eTBVS, and remaining length of stay appropriate tests depending on the distribution will be used (t-Test or Mann-Whitney-U-test for continuous variables and chi-square tests or Fisher-Boschloo-tests for categorical variables).

To evaluate whether disagreement between the physicians response to the question what they thought the intravascular volume of the patient was doing (increasing, decreasing, no change, treating physicians assessment Day 3) and the direction of measured change in TBVS is associated with a longer remaining length of stay, a t-test or Mann-Whitney-U-test depending on the distribution will be used. A measured change in TBVS of more than 5% between Day 1 and 3 was determined as a significant change.

To evaluate (by an adjudication committee) whether clinical decision making would have been affected by adding FAST GFR and PV measurements to clinical routine, the following questions were to be answered:

- How would you alter the intensity of Diuretic Therapy given on Day 1 and Day 3?
- How would you alter the intensity of RAASI Therapy given Day 1 and Day 3?  
How would you alter the intensity of Beta Blocker Therapy given Day 1 and Day 3?
- How would you alter the intensity of other GDMT given Day 1 and Day 3?

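### The 10%/30% count for day 1 to day 3 volume changes uses a window that closes as the measured change nears zero; on the ratio scale the same count is too lenient

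*SAP*

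**What the plan says.** SAP 7.7.1 asks whether the day 1 to day 3 changes in estimated PV and TBV reflect the changes in the measured values. It names absolute and relative change for both volumes and adds the Strauss formula for PV. Three measures are planned.

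- Bland-Altman plots without preset limits: "These plots will be analysed exploratory, since no appropriate values for limits of agreements are available".
- A count: "The amount of values within 10% and within 30% of the measured values will also be determined".
- The Obuchowski accuracy index with a 95% confidence interval.

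The same section uses a similar count for the volumes themselves on day 1 and on day 3: "The amount of values within 15% and within 30% of the measured values will also be determined".

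SAP 7.2 writes the Strauss change as the ratio PV_2/PV_1 x 100 and adds: "Plasma volume change will also be calculated via the ratios of ePV by the Kaplan-Hakim-Formula". No ratio version is given for TBV. The SAP does not say whether the 10%/30% count applies to the difference or to the ratio. It gives no rule for a measured change near zero or for estimated and measured changes of opposite sign.

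**The concern.** A percentage window works for volumes, because the denominator is litres. A change over 48 hours can be small or zero. For a measured change of -2%, the 10% window runs from -1.8% to -2.2%; for a measured change of zero it has no width. The SAP expects patients with small changes: in its analysis of physician disagreement, "A measured change in TBVS of more than 5% between Day 1 and 3 was determined as a significant change", so changes up to 5% are treated there as not significant.

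On the difference scale, the count therefore mixes the accuracy of the formula with the mix of patients. The same formula could look poor in a sample with small changes and fair in one with large changes. On the ratio scale the opposite happens: nearly everything lies within the window, including predictions that carry no information. At stake is how far a reader can trust the only agreement measure for changes that has a preset tolerance.

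**Working it through.** The SAP gives no expected percentage for this count, so there is no figure to reproduce. The distribution of changes and the error of the formulas are also not in the documents. The inputs below are assumptions, shown over a range.

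**Inputs.** Measured percent change d is normal with mean 0, -3, -5 or -10% and SD 4, 6, 8 or 10%. The formula is unbiased with error SD s of 1 or 2 percentage points. Window fraction k is 0.10 or 0.30 (SAP 7.7.1).

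**Step 1: difference scale, one patient.** P(within window | d) = 2Φ(k|d|/s) - 1. With k = 0.10 and s = 1:

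| Measured change | 10% window | P(within) |
|---|---|---|
| 2% | ±0.2 points | 16% |
| 5% | ±0.5 points | 38% |
| 10% | ±1 point | 68% |
| 20% | ±2 points | 95% |

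The error SD is the same in every row. Only the measured change differs.

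**Step 2: difference scale, averaged over patients.** Integrating Step 1 over the distribution of d:

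| Error SD | Mean -3%, SD 6%: within 10% / 30% | All 16 combinations: within 10% |
|---|---|---|
| 1 point | 38% / 71% | 24% to 65% |
| 2 points | 21% / 50% | 13% to 41% |

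The lowest score comes at mean 0, SD 4%. If all 50 planned patients had both measurements, 24-65% would be about 12 to 32 patients, for one and the same formula.

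**Step 3: the same check in mL.** The only spread of a measured PV change in the documents is from the Phase 2b albumin infusion cohort (Protocol 3.1.3.4): "the average plasma volume increase was 324 ml with an SD of 49mL". It is not the error of an estimating formula and serves only to show scale. With an error SD of 49 mL and a measured change of 100 mL, the windows are ±10 and ±30 mL, and the shares outside are 2[1 - Φ(10/49)] = 84% and 2[1 - Φ(30/49)] = 54%. At 324 mL they are still 51% and 5%. Averaged over assumed changes with mean 0 to -400 mL and SD 150 to 450 mL, the share outside 10% is 42-81% for error SD 49 mL, 17-66% for 25 mL and 2-38% for 10 mL.

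**Step 4: ratio scale.** Scored as PV_2/PV_1, a formula with error SD 1 or 2 points lies within 10% in practically every patient. But take a formula that always predicts a ratio of 1. It is within 10% when the measured ratio lies between 1/1.1 = 0.909 and 1/0.9 = 1.111, that is, for d from -9.1% to +11.1%. At mean -3%, SD 6%: Φ(2.35) - Φ(-1.02) = 84%. Over the 16 combinations the range is 41-99%. Within 30% it scores at least 90% throughout.

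**Step 5: a fixed bound.** With a bound of b points, P(within) = 2Φ(b/s) - 1, which does not contain d. For b = 5 this is over 99.9% at s = 1 and 98.8% at s = 2, in every combination. A no-change prediction scores 54% within 5 points and 86% within 10 points at mean -3%, SD 6%. A fixed bound therefore also needs a reference value beside it.

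**The case against.** The strongest reply has four parts.

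1. *The scale is open.* The SAP defines two forms of PV change as ratios, and these have no denominator near zero. This stands, and it limits the claim: division by a near-zero change is not certain for every form. It does not rescue the count, because Step 4 shows that the ratio form barely separates a good formula from an empty one. TBV has no ratio form.
2. *Nothing is passed or failed.* A reader might infer that an almost exact formula would be reported as failing, or that the trial would conclude that estimated volumes do not follow the measured ones. The documents do not support this. No percentage is set as failure, SAP 7.1 calls all analyses descriptive, and the objective is secondary.
3. *Other measures stand beside it.* Bland-Altman plots show bias and spread directly, and SAP 8 says that they were chosen because they better address clinical equivalence. The Obuchowski index uses ranks. Neither divides by the measured change, and an accurate formula would look good on both. This also stands, although the plots carry no limits and the index measures ranking, not closeness.
4. *The sizes are assumed.* This stands too. With large changes and a very small error (mean -400 mL, SD 150 mL, error SD 10 mL), only 2% of patients fall outside 10%.

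It is also fair to say that the SAP's 5% is no agreement margin. It defines a significant change in TBVS, which is scaled to ideal volume, in a different analysis.

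**Conclusion.** The concern holds in a limited form. On the difference scale, the count depends heavily on how many patients changed little: about 24-65% within 10% for a formula with 1-point error and 13-41% with 2-point error, under assumed changes with mean 0 to -10% and SD 4 to 10%. On the ratio scale it is too lenient: 41-99% within 10% for a prediction of no change. The SAP does not say which scale applies, and neither gives a count that can be read as agreement.

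The consequence is modest. One descriptive secondary measure could mislead, and a reader who has the Bland-Altman plots and the index can see past it. The shape of the problem follows from the rule itself; the percentages rest on normal changes and unbiased normal errors that the documents do not supply. The 15%/30% count for volumes on a single day is not affected.

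**What to change.** In SAP 7.7.1, for changes only:

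- Replace the 10%/30% count by the share of patients whose estimated and measured percent changes differ by no more than a prespecified number of percentage points, for example 5 and 10 (or a fixed number of mL for absolute change).
- Convert the Strauss and Kaplan-Hakim ratios to percent change before scoring, so that all forms share one scale.
- Report the share with the same direction of change among patients whose measured change exceeds 5%.
- Report the score that a no-change prediction would obtain, as the reference.
- Label the bounds exploratory, since the SAP itself states that no suitable limits are available.

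The cost is SAP wording and a few lines of code; no new data are needed. The downside is that the bounds have no established clinical source, and the 5% cut is borrowed from the TBVS analysis. The direction share and the no-change reference let readers judge the result without relying on one bound.

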Table 9: Clinical data
Total 24h dose of i. v. furosemide (from 06:00am same day to 06:00 am next day) (mg)
Total 24h dose of i. v. torasemide (from 06:00am same day to 06:00 am next day) (mg)
Total 24h dose of p. o. furosemide (from 06:00am same day to 06:00 am next day) (mg)
Total 24h dose of p. o. torasemide (from 06:00am same day to 06:00 am next day) (mg)
Application of any thiazide diuretic?

Dialysis/ultrafiltration performed? (from 06:00am to 06:00 am next day)  
 iv. fluids (NaCl, balanced electrolytes) (from 06:00am to 06:00 am next day) (L/24 h)

Is the total dosage of diuretics (administered from 06:00 am same day to 06:00 am next day) increased compared to previous 24 h dosage? (e. g. increasing loop diuretics or adding thiazide diuretics or aldosterone antagonists)?

Is the total dosage of diuretics (administered from 06:00 am same day to 06:00 am next day) decreased compared to previous 24 h dosage? (e. g. decreasing loop diuretics or removing thiazide diuretics or aldosterone antagonists)?

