### Sample size

The primary objective is to assess the safety and function of the FAST PV and mGFR Technology in hospitalized patients with heart failure. This is a phase II trial. It is planned to enroll 50 eligible patients. No formal hypothesis test is performed to assess the primary objective. This is justified as follows:

1. Both function and safety cannot be uniquely assessed by one specific endpoint, but there exist several relevant endpoints and endpoint-related criteria which must be investigated in order to assess the global function and safety.
2. For reasons of feasibility, the studies sample size is limited to 50 patients which is an adequate number in the context of a phase II trial. However, this limited number does not allow to address a complex multiple testing problem with adequate power.

Therefore, all analyses are purely descriptive.

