#### 4.3.2 Safety/Tolerability

- Length of stay, dialysis/ultrafiltration requirement, or rehospitalization within 30 days, or mortality
- Laboratory values (Serum creatinine (mg/dl), Hematocrit (%), creatine phosphokinase (CPK) (U/l), NT-proBNP (ng/l), Alanine aminotransferase (ALT) (U/l), Aspartate aminotransferase (AST) (U/l), Alkaline phosphatase (AP) (U/l), bilirubin, total and direct (mg/dl), INR (dimensionless)) collected on day 1, 3, 5 (except for serum creatinine which is collected on all days and hematocrit which is only collected on day 1)
- Occurrence of AEs and SAEs
- Routine clinical parameters (Serum creatinine on admission (mg/dl), Baseline serum creatinine (nadir from inspection of previous, lab values or by primary care physician) (mg/dl), Serum creatinine (mg/dl), Serum sodium (mmol/l), Serum potassium (mmol/l), eGFR (CKD-EPI) (ml/min/1.73 m^2), Hemoglobin (g/dl), Serum-Albumin (g/dl), Urine output (0:00 - 24:00 on the indicated day) (ml/24 h) (if, incomplete, extrapolate the available time period to 24 hours), Chest X-ray: evidence of pulmonary congestion, Chest X-ray: evidence of pleural effusion, Chest X-ray: evidence of cardiomegaly, Alanine aminotransferase (ALT) (U/l), Aspartate aminotransferase (AST) (U/l), Alkaline phosphatase (AP) (U/l), Bilirubin, total and direct (mg/dl))

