## **7 Statistical analyses / methods**

### **7.1 General remarks**

The primary objective is to assess the safety and function of the FAST PV and mGFR Technology in hospitalized patients with heart failure. This is a phase II trial. No formal hypothesis test is performed to assess the primary objective. This is justified as follows: 1. Both function and safety cannot be uniquely assessed by one specific endpoint, but there exist several relevant endpoints and endpoint-related criteria which must be investigated in order to assess the global function and safety. 2. For reasons of feasibility, the studies sample size is limited to 50 patients which is an adequate number in the context of a phase II trial. However, this limited number does not allow to address a complex multiple testing problem with adequate power.

Therefore, all analyses including p values are purely descriptive. The aim is to generate new hypotheses to be tested in subsequent phase III trials.

For continuous variables descriptive statistics include mean, standard deviation, median, inter quartile range and range. For categorical variables descriptive statistics include absolute and relative frequencies.

Due to the low number of patients in one of the centers, no adjustment for center will be done in the analyses.

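### SAP 7.7.1 gives dialysis/ultrafiltration no start time in models whose predictor is known only on Day 3, and gives the length-of-stay model no rule for in-hospital death

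*SAP*

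**What the plan says.** SAP 7.7.1 asks whether volume measurements predict four outcomes, which SAP 4.3.2 lists as "Length of stay, dialysis/ultrafiltration requirement, or rehospitalization within 30 days, or mortality". The methods are "linear (remaining length of stay), logistic (dialysis/ultrafiltration, rehospitalization within 30 days) or Cox-regression models (mortality".

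Each outcome gets four predictor sets. The first is "changes of mPV and mTBV from day 1 to day 3 (first model", the second is the same change in mPVS and mTBVS, and the last two are "mPVS and mTBVS at day 1 (third model) and day 3 (fourth model) as independent variables".

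Only length of stay has a time origin: "remaining length of stay at the given day (i.e. remaining length of stay starting with day 1 or with day 3". The SAP does not say which of the two days applies to the change models. No start is given for dialysis/ultrafiltration; the 30-day limit is attached to rehospitalization. Neither document says how a death in hospital enters the stay analysis.

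Dialysis/ultrafiltration is captured in Protocol 4.4, Table 9, as "Dialysis/ultrafiltration performed? (from 06:00am to 06:00 am next day". The schedule of events marks these clinical data for Days 1 to 5.

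**The concern.** The second dose follows the first by 48 hours, give or take 5, so the predictors in models 1, 2 and 4 do not exist until then. Ultrafiltration removes plasma volume. A session between the two measurements is therefore one of the causes of the predictor. If it is also counted as an outcome, the model can show an association between falling volume and dialysis/ultrafiltration that has no predictive content.

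The second gap is in the stay model. A patient who dies in hospital has an observed last hospital day, so the simplest derivation gives that patient a short remaining stay, the value that otherwise marks a quick recovery. If the same predictor values go with longer stay and with higher mortality, the slope shrinks.

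What is at stake is the hypothesis carried forward. SAP 7.1 says the trial is meant to generate hypotheses for phase III, and whether volume change predicts outcome is an obvious candidate.

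**Working it through.** There is no figure in the plan to reproduce. The SAP states "It is planned to enroll 50 eligible patients", a number set by feasibility without power or effect size. The check is therefore a reading of time order, then an illustration under assumed rates.

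**Time order**

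- Models 1 and 2 (change) and model 4 (Day 3 status): predictor fixed at Day 3, dialysis/ultrafiltration outcome open from Day 1. The order is wrong for any event before Day 3.
- Model 3 (Day 1 status): the predictor comes first, so the order is right.
- Elsewhere SAP 7.7.1 does set forward windows: 72 and 48 hours for AKI, and 24 to 48 hours for ultrafiltration within the diuretic-refractory endpoint. The gap is particular to these models, and SAP section 8 does not close it.
- Early events are possible. Only chronic dialysis is an exclusion, and the adjudication questions in Protocol 4.2 and SAP 1.1 ask about dialysis/ultrafiltration between Days 1 and 3.

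**A. Dialysis/ultrafiltration, with no true prediction**

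Assumptions, none from the documents: 6% have ultrafiltration before Day 3; 4% or 10% have it later, unrelated to the change; early ultrafiltration shifts the change by s = −0.5 or −1 SD. The share of counted events that are early is

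share = pre / (pre + post − pre × post)

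For 6% and 4% this is 0.06/0.0976 = 0.615. For 6% and 10% it is 0.06/0.154 = 0.390. Events then differ from non-events by about s × share in mean, so the odds ratio (OR) per SD is roughly exp(s × share). The simulation used 400,000 patients for each OR and 800 samples of n = 50 for rejection at nominal 5%.

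| Later rate | s | exp(s × share) | Simulated OR, all events | Rejection, all events | Rejection, post-Day 3 only |
|---|---|---|---|---|---|
| 4% | −0.5 | 0.74 | 0.74 | 11.1% | 4.4% |
| 4% | −1 | 0.54 | 0.55 | 30.7% | 7.9% |
| 10% | −0.5 | 0.82 | 0.82 | 8.5% | 5.0% |
| 10% | −1 | 0.68 | 0.69 | 19.6% | 4.7% |

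The hand formula and the simulation agree. With 2% early the OR is 0.71 to 0.93; with 10% early it is 0.50 to 0.77. With none early it is 0.99 to 1.01. Counting only events after Day 3, and leaving out patients with earlier ones, gives 0.99 to 1.01 in every scenario.

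**B. Remaining stay, true slope +1.00 day per SD**

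Assumptions: mean stay 8 days, SD 5, death uniform over 0 to 6 days after Day 3, death taken as end of stay. Death risk rises with the predictor, in the same direction as stay, with an OR of 1, 2 or 3 per SD.

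| In-hospital deaths (of 50) | OR 1 | OR 2 | OR 3 |
|---|---|---|---|
| 0% (0) | 1.00 | 1.00 | 1.01 |
| 2% (1) | 0.99 | 0.89 | 0.85 |
| 6% (3) | 0.96 | 0.72 | 0.60 |
| 10% (5) | 0.90 | 0.56 | 0.38 |

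Using survivors only returns 0.99 to 1.01, but only because the simulation makes stay independent of death given the predictor. That cannot be relied on in real data.

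**C. Would such events occur?** The chance of at least one in 50 is 1 − (1 − p)^50: 64% at p = 2%, 87% at 4%, 95.5% at 6%.

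**The case against.** The strongest reply is that the SAP is silent and not wrong. It nowhere instructs the analyst to count early ultrafiltration or to enter a death as a short stay; deaths could be left out or censored. That stands, and it is why the point is conditional. Silence still leaves the choice to be made after the data are seen, and the literal reading of the dialysis/ultrafiltration outcome includes Days 1 and 2.

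Early events may also be few. Cardiogenic shock, vasopressors, intravenous inotropes or vasodilators, and hypotension are exclusions, and ICU admission before the second dose may lead to withdrawal. This limits the size but does not rule such events out.

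A reader might infer that the mortality model is biased in the same way. The documents do not support this. A patient who dies before Day 3 has no change and no Day 3 value, and SAP 5.1 does not replace missing secondary values, so that patient drops out of models 1, 2 and 4. Moving the Cox origin by about 48 hours leaves the order of survival times essentially unchanged.

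A reader might also infer that the stay slope could reverse. No scenario shows it: the lowest value is 0.38, still positive.

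Finally, SAP 7.1 says "Therefore, all analyses including p values are purely descriptive", and a logistic model with few events and two related predictors is unstable whatever its time origin. Both are fair and lower the weight of the point. Neither corrects a wrong time order.

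**Conclusion.** The concern holds as a conditional one. In models 1, 2 and 4 the dialysis/ultrafiltration outcome is not confined to the time after its predictor, and the stay model has no rule for in-hospital death. A reader might conclude that the results are biased; the documents do not support that, because with no ultrafiltration before Day 3 and no in-hospital death there is no bias, and no rates are given.

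If 6% (3 of 50) had early ultrafiltration, a null relation would appear as an OR of about 0.55 to 0.82 per SD. If 2 to 6% (1 to 3 of 50) died in hospital and death ended the stay, a true slope of 1.00 would appear as about 0.60 to 0.99. Both ranges rest on the assumed rates, shifts and death associations above.

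The dialysis/ultrafiltration point does not touch model 3. The stay point applies wherever remaining stay is analysed. The primary safety and FD003 stability results are unaffected. The change is worth making before analysis.

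**What to change.** Change SAP 7.7.1 as follows.

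- **Dialysis/ultrafiltration, models 1, 2 and 4:** count only events first recorded after the Day 3 measurement. Leave patients with an earlier event out of this model and list them.
- **Day 3 window:** Table 9 records 06:00 to 06:00 without clock time, so a session on Day 3 cannot always be placed before or after the dose. State the rule, for example to use source times or to start with the next 06:00 window. State the end of the outcome window too, since this item is scheduled only to Day 5.
- **Remaining stay:** replace the linear model by time to live discharge from a stated origin (the Day 3 measurement for models 1, 2 and 4), with in-hospital death as a competing event. Ranking deaths worst is the simpler alternative.
- **Other uses of remaining stay:** apply the same handling in the two later comparisons in SAP 7.7.1, improving versus worsening mGFR and physician disagreement with the measured volume change.
- **Mortality:** state the Cox origin, for completeness only.

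The cost is SAP wording, some programming and possibly a look-up of Day 3 dialysis times. The drawback is that a few early events leave a model that is already sparse; listing them keeps them visible.
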